7.1.4 Treatment Interruptions during RT

Although we do not anticipate side effects resulting in a break during treatment, there is the low possibility of Radiation Induced Liver Disease (RILD) or bleeding secondary to radiation treatment. Prior retrospective studies have been used to define our current dose limitation guidelines to reduce risk of RILD to a negligible level. HIGRT will be discontinued at the discretion of the treating physician according to best clinical practice.

7.1.5 Concomitant Medications/Therapies

Patients will receive no additional HCC directed therapy (i.e. sorafenib) during active protocol participation. There are no limitations regarding what treatment they can receive after treatment completion including HCC directed therapies and/or repeat ablation or HIGRT treatments if needed.

7.2 Rationale for Selection of Dose, Regimen, and Treatment Duration

HIGRT dose will be defined depending on primary tumor size and risk to neighboring organs at risk (OAR); see Section 9.3 for specifics. HIGRT dose and constraints are based on prior research into treated organ tolerance¹¹ and optimal treatment strategies^{12, 13}.

7.3 Data collection for Quality of Life Surveys (Appendix)

Two surveys will be used to collect baseline, 1 month, 3 month and 6 month QOL information. European Organization for Research and Treatment of Cancer Quality of Life Questionnaire Core-30 (QLQ-C30) will be used to assess general symptom burden, social, financial and psychological burden. The Functional Assessment of Cancer Therapy-Hepatobiliary (FACT-Hep) survey will be used to assess liver specific symptom burden. Both surveys will be collected at baseline (prior to initiation of any therapy) and at 1, 3 and 6 month time marks. Good faith effort will be made to collect survey data in person and on paper if at all possible. If in person or on paper survey collection is not possible, oral survey data collect is allowed by authorized study staff either in person or on the phone. Good faith effort to collect data will allow that surveys may be mailed to subjects. Alternatively surveys may be completed via a secure link electronically. Surveys will be collected within a 2 week period of the planned time mark.

7.4 Definition of Evaluable Subjects, On Study, and End of Study

Patient are “on study” during the intervention time period (either ablation or HIGRT) and the 6-month follow up while additional survey data is being collected. End of study is defined as 180 days post-therapy (+/- 30 days) at the time of the last follow up survey. We will continue to collect patient data from the EHR for 5 years after study enrollment or until death. For the purposes of the primary endpoint of QOL, a patient who has received either ablation or HIGRT and completed at least the baseline and month 1 follow up QOL surveys will be analyzed.

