2.2.3 Data Analysis and Statistical Considerations

Ninety patients will be randomized with equal allocation to the two arms. Randomization will be stratified by whether the baseline global QOL score is < 60 or ≥ 60 , where QOL is measured by the EORTC QLQ-C30 scale (i.e., the European Organization for Research and Treatment of Cancer Quality of Life Questionnaire Core-30) which has a score range of 0-100. The primary outcome is the change in QOL from baseline to 1 month. We anticipate that approximately 10% of the accrued patients will be withdrawn before 1 month, leaving 80 evaluable patients to be used in the statistical analyses. The general linear model will be used to test for an arm effect (in patients receiving PLA vs HIGRT) by regressing the change in QOL on arm, controlling for the baseline value of QOL and the Child Pugh score. To calculate the power of the arm effect (in patients receiving PLA vs HIGRT) on change in QOL, we first note that the standard deviation of a normally distributed change score (SD_c) depends upon the SD of the pre-score, the SD of the post-score, and the Pearson correlation (ρ) between the two scores. If the SD's of the pre-score and the post-score are assumed equal and the correlation between them is 0.50, then $SD_c = SD$. For purposes of the power calculation, we assume that $SD=10$ and $\rho = 0.5$; therefore $SD_c = 10$. Assuming 40 evaluable patients per arm, the two-sample t-test (1-sided alpha = 0.10) of an arm difference in change across time in QOL has power 0.82 when the true arm difference in change score is 5 (i.e., 50% of SD_c). An arm difference of 50% of a standard deviation of an outcome variable is generally considered to be a "medium"-sized effect. In order to have 80 evaluable patients, 90 patients will be accrued (assuming ~10% drop out prior to the 1 month EOTRC QOL-C30 questionnaire).

After randomization, patients who have consented to study, but in the clinical judgement of the treating physician are no longer candidates for the randomized treatment, will continue to be evaluable for all study endpoints if treated with MWA or HIGRT (per PI approval). The primary analysis will be intent-to-treat (i.e., treatment arm as randomized). A sensitivity analysis will be conducted with patients categorized by treatment received.

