Ninety patients will be randomized with equal allocation to the two arms. Randomization will be stratified by whether the baseline global QOL score is < 60 or ≥ 60 , where QOL is measured by the EORTC QLQ-C30 scale. We anticipate that approximately 10% of the accrued patients will withdraw before 1 month, leaving 80 evaluable patients to be used in the statistical analyses. The general linear model will be used to test for an arm effect (in patients receiving PLA vs HIGRT) by regressing change across time in QOL on arm, controlling for the baseline value of QOL, Child Pugh score, and time between baseline and end of treatment. To calculate the power of the arm effect (in patients receiving PLA vs HIGRT) on change in QOL, we first note that the standard deviation of a normally distributed change score (SD_C) depends upon the SD of the pre-score, the SD of the post-score, and the Pearson correlation (ρ) between the two scores. If the SD's of the pre-score and the post-score are assumed equal and the correlation between them is 0.50, then $SD_C = SD$. For purposes of the power calculation we assume that $SD=10$ and $\rho = 0.5$; therefore $SD_C = 10$. Assuming 40 evaluable patients per arm, the two-sample t-test (1-sided alpha = 0.10) of an arm difference in change across time in QOL has power 0.82 when the true arm difference in change score is 5 (i.e., 50% of SD_C). An arm difference of 50% of a standard deviation of an outcome variable is generally considered to be a "medium"-sized effect. In order to have 40 evaluable patients per treatment arm, 90 patients will be accrued (assuming drop out prior to the 1 month EORTC QOL-C30 questionnaire).

After randomization, patients may decline the randomized treatment but will continue to be evaluable for all study outcomes if treated with MWA or HIGRT. All endpoints will be analyzed per randomized arm and per treatment delivered. If the patient does not receive either SBRT or MWA, the patient will be withdrawn from the study.

Secondary Endpoints:

[figure not shown]

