10.7.2 Follow-up Requirements for Early Withdrawal

Subjects who withdraw prior to study completion will be followed for primary and secondary end points via an intention to treat analysis. All attempts will be made to complete QOL surveys as appropriate.

Subjects may decline to complete surveys at any time during study participation; declining to complete surveys will be recorded and will not be considered a reportable protocol deviation.

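### The primary analysis is labelled intent-to-treat but is defined on treated patients with a month 1 survey, and no planned analysis tests the effect of missing month 1 scores

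*Combined protocol and SAP*

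**What the plan says.** Five sections bear on who enters the primary comparison.

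- **Section 2.2.3:** "The primary analysis will be intent-to-treat (i.e., treatment arm as randomized"). The one sensitivity analysis named is: "A sensitivity analysis will be conducted with patients categorized by treatment received".
- **Section 4, Primary Endpoint:** it expects about 10% of patients to be lost before month 1, "leaving 80 evaluable patients to be used in the statistical analyses". Patients who switch to the other study treatment stay evaluable. For those who get neither: "If the patient does not receive either SBRT or MWA, the patient will be withdrawn from the study".
- **Section 7.4:** the primary endpoint is analysed for "a patient who has received either ablation or HIGRT and completed at least the baseline and month 1 follow up QOL surveys".
- **Section 10.7.2:** "Subjects who withdraw prior to study completion will be followed for primary and secondary end points via an intention to treat analysis". Attempts will be made to obtain their surveys, although a subject may decline a survey at any time.
- **Section 10.7.3:** subjects who withdraw before protocol therapy may be replaced. It does not say what becomes of the replaced patient in the analysis.

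The primary model regresses change in QOL on arm. Section 2.2.3 adjusts for baseline QOL and Child Pugh score. Section 4 has a longer list: "controlling for the baseline value of QOL, Child Pugh score, and time between baseline and end of treatment".

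**The concern.** A reader told that the result is intent-to-treat will assume that every randomised patient is counted or accounted for. Under Section 7.4, a patient can leave the primary comparison because of what happens after randomisation: not being treated, withdrawing, dying, or not answering at month 1. Section 10.7.1 lists adverse events and disease progression among the reasons for withdrawal, and both plausibly go with poorer QOL.

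At stake is whether the arm difference among those who remain equals the difference between the arms as randomised. If loss depends on how patients fare and differs by arm, the two can part, and nothing in the plan would reveal it.

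**Working it through.** **1. The plan's own figure.** Inputs from Sections 2.2.3 and 4: 40 evaluable per arm, difference 5, SD of change 10, one-sided alpha 0.10. The standard error is 10 × √(1/40 + 1/40) = 2.236, and the noncentrality is 5 / 2.236 = 2.236 on 78 degrees of freedom. Power by noncentral t is 0.827, against 0.82 stated. The sample size is not in question.

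**2. Planned loss.** 90 randomised less 80 evaluable is 10 patients, and 10/90 = 11%. This covers loss for any reason; Section 7.4 does not cause all of it.

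**3. Do the sections agree?**

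| Patient | 2.2.3 and 4 | 7.4 | 10.7.2 and 10.7.3 |
|---|---|---|---|
| Treated in the other arm, month 1 survey done | In, as randomised | In | No conflict |
| Treated, withdraws, month 1 survey obtained | In | In | In |
| Treated, no month 1 survey | Expected loss | Out | To be followed; no method given for the missing score |
| Never treated | Withdrawn | Out | To be followed under intention to treat, yet may be replaced |

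The last row is a direct conflict. The third is a gap in method.

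**4. When is the complete-case regression safe?** A change score needs an observed month 1 value. Dropping the other patients is safe if, within arm and given the covariates, loss has nothing further to do with the month 1 score. It also gives no bias in the arm difference if loss is balanced and the lost patients fare alike in both arms. Nothing planned checks either condition:
- The treatment-received analysis regroups patients and recovers no missing score.
- The rule in Section 10.6 for patients lost to follow-up is censoring, which has no meaning for a change score at a fixed time.
- No rule is given for deaths before month 1.

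**5. Illustration (assumed, not from the documents).** No true difference over all 90 patients; 45 per arm; 6 lost from HIGRT and 4 from PLA; lost patients worse than observed ones by the same gap in both arms; SD 10.

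Shift among completers = (6/45 − 4/45) × gap. Standard error = 10 × √(1/39 + 1/41) = 2.24.

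| Gap (points) | Shift towards HIGRT | One-sided error rate (nominal 10%) | Error rate if split is 4 HIGRT, 6 PLA |
|---|---|---|---|
| 5 | 0.22 | 11.8% | 8.4% |
| 10 | 0.44 | 13.9% | 7.0% |
| 20 | 0.89 | 18.8% | 4.7% |

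A 5/5 split gives (5/45 − 5/45) × gap = 0.

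If loss is unrelated to arm, the hypergeometric probability of a 5/5 split is 26% and of a 6/4 split in either direction 42%. Such chance shifts average out over repeated trials; a systematic one needs the arm to affect who is lost or how the lost patients fare. Baseline adjustment removes whatever part of the gap baseline QOL and Child Pugh explain, so the table is for an unadjusted comparison.

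**The case against.** The strongest reply is that the label is defined. Section 2.2.3 glosses intent-to-treat as grouping by randomised arm, and the same section openly expects 80 of 90 patients in the analysis. Section 7.4 then says who those patients are. Read this way, Sections 2.2.3, 4 and 7.4 fit together as an as-randomised analysis of treated completers. That stands, and a reader who infers a plainly broken promise in Section 2.2.3 goes too far. What remains is that such a set is conventionally called modified intent-to-treat, and that Section 10.7.2 still says something different about untreated patients.

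A reader might also infer that the plan throws away month 1 scores from untreated patients. The documents do not support this as a known loss. Sections 4 and 11.2 time the survey from treatment, so an untreated patient has no scheduled month 1 score. How many such scores would be obtained under Section 10.7.2 is not stated.

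Complete-case analysis is not in itself a fault, for the reasons in step 4. The plan also works to limit loss: Section 7.3 permits mail and electronic surveys, and "oral survey data collect is allowed by authorized study staff either in person or on the phone". These measures should reduce missing scores, but they do not settle who is analysed or test the effect of those still missing.

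Finally, the gap and the split in the illustration are assumed, and the shift is small against the 5-point target. Both points are right.

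**Conclusion.** The concern holds as a matter of labelling, consistency and missing-data planning. The primary set is treated completers as randomised. It should be called modified intent-to-treat, it conflicts with Section 10.7.2 for untreated patients, and the status of replaced patients is left open; under Section 7.4, those never treated drop out of the comparison. With about 11% loss planned, and withdrawal reasons that may relate to QOL, the absence of any sensitivity analysis for missing month 1 scores is a real gap.

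One might infer that the trial will be biased towards HIGRT, or that its error rate is 19%. The documents support neither. The figures of about 12% to 19%, or about 8% to 5% with the split reversed, rest on an assumed 6/4 split and an assumed gap of 5 to 20 points. The actual size and direction are unknown. Nor do the documents require all randomised patients to be the primary set; that is a choice of a different estimand. The point should be fixed, and it does not affect the sample size.

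**What to change.** 1. **Label and reconcile.** Bring Sections 2.2.3, 4, 7.4, 10.7.2 and 10.7.3 into line. Call the Section 7.4 set modified intent-to-treat (treated completers, as randomised). State that untreated and replaced patients remain in the all-randomised set, and report them by arm with reasons.
2. **Add one sensitivity analysis.** Include all randomised patients with a baseline score, by assigned arm. Use any month 1 score obtained under Section 10.7.2 and impute the rest, with delta shifts varied separately by arm until the conclusion changes (a tipping-point analysis). Use the Section 2.2.3 covariates, because the time to end of treatment in Section 4 is undefined for an untreated patient.
3. **Deaths before month 1.** State how they enter this analysis and report them by arm.

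Making the all-randomised set primary is optional. It needs a stated survey-time convention for untreated patients, and it dilutes the contrast slightly. If untreated patients show no arm difference and no replacements are added, 4 of them giving scores makes the difference 5 × 80/84 = 4.76 with 42 per arm, for power of about 0.81. With all 10 it is 5 × 80/90 = 4.44 with 45 per arm, for power of about 0.79. The plan states 0.82.

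The cost of steps 1 to 3 is wording changes and one extra analysis. The sample size stays at 90.

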7.5 Early Study Termination

This study can be terminated at any time for any reason by the PI. If this occurs, all subjects on study should be notified as soon as possible. Additional procedures and/or follow up should occur in accordance with Section 11.7, which describes procedures and process for prematurely withdrawn patients.

RADIATION THERAPY

8.1 Type, Classification, Location, and Short Description

Therapy is high dose image guided radiotherapy (HIGRT) delivered in 5-10 fractions.

8.2 Equipment

A linear accelerator with on board imaging is used for treatment delivery.

8.3 Dose Specifications

The treatment dose is 50 Gy in 5 or 10 fractions. Please see section 9.6 for more details.

8.4 Localization, Simulation

All patients will undergo standard of care CT-based treatment planning in custom made immobilization devices. CT scan range must allow simultaneous view of the patient anatomy and fiducial system for stereotactic targeting (if used) and be adequate to ensure contouring of all targeted lesions, as well as necessary organs at risk (OAR). High-resolution CT scans should be obtained with uniform slice thickness of $\leq 3\text{mm}$ throughout.

The use of IV contrast is preferred. If there is a contraindication for IV contrast an abdominal MRI must be available for treatment planning. The use of other contrast agents is left to the discretion of the treating oncologist. If possible, the use of triphasic (arterial, portal venous, and delayed imaging) is recommended using a flow rate of 4-5ml/sec and 175ml of contrast.

Regions of high vascular contrast in the planning dataset are recommended to be converted to water equivalent density if used for planning (at the discretion of the treating physician). Planning datasets without intravenous contrast may be used for dose calculation.

Ideally a liver-specific MRI will be available and possibly fused with the treatment planning CT scan for target delineation.

8.5 Respiratory Motion Assessment and Management

All respiratory motion should be evaluated by appropriate means including 4D CT scan, imaging of implanted fiducial marker, or fluoroscopy at the time of simulation.

Respiratory motion management (RMM) including abdominal compression, active breathing control, breath hold, end expiratory gating, or fiducial marker tracking, is recommended for any lesion to be treated with motion $> 5\text{mm}$. A recommended approach would be to use an ITV technique for motion $< 1\text{cm}$, but for motion $> 1\text{cm}$ (typically too large for a free breathing ITV) motion management including but not limited to abdominal compression, active-breathing control (ABC), gating, breath hold, etc. should be used.

8.6 Treatment Planning/Target Volumes

CT images (ideally triphasic images) will be registered to MRI images (by soft tissue alignment) to assist in contouring the GTV. Registration will be performed with the best fit liver-to-liver image registration focusing on the region of the PTV if deformation or rotation occurs between scans.

The GTV represents the target lesion and should be identified on the arterial, portal venous, and delayed CT image sets (if multiple phase CT images are available) as well as on MRI images.

An ITV expansion of the GTV will be created to fully account for the magnitude of the motion observed in the 4D simulation evaluation. If multiple contrast phases are available from CT simulation these will be registered to bony anatomy to verify that the GTV remains encompassed by the ITV.

The ITV will be expanded by 5-10mm radially and 7-10mm superior/inferiorly to arrive at the PTV.

The treatment dose is 50 Gy in 5 or 10 fractions over 2 or 3 weeks, respectively. Lesions in close proximity to a GI structure (colon, small bowel, duodenum, stomach), in a patient with Child-Turcotte-Pugh (CTP) classification B, or a patient with prior radiotherapy to the abdomen will be treated with 50Gy in 10 fractions. Fractionation determination is at the discretion of the treating physician.

Conformal 3D or arc radiotherapy, IMRT or VMAT are acceptable methods of treatment delivery.

All patients must be imaged prior to treatment with volumetric imaging.

8.6.1 General Considerations

A variety of planning techniques can be used to deliver HIGRT for each lesion. General guidelines include the following:

- Multiple coplanar or non-coplanar beam arrangements are acceptable.
- A minimum field dimension of 3 cm should be observed treating small lesions.
- Dynamic conformal arcs are acceptable.
- The prescription isodose line covering 95% the PTV will generally be 80-90% but may range from 60-90% where the maximum dose is 100%. As a result, a “hotspot” will exist within the PTV that is equal to the prescription dose divided by the prescription isodose line (i.e., $45\text{Gy}/0.6 = 75\text{Gy}$ when 45Gy is prescribed to the 60% isodose).
- Doses higher than the prescription isodose (i.e., hotspots) should be manipulated to occur within the target.

8.6.2 Dose calculations

All dose distributions shall include corrections for tissue heterogeneities. RPC approved algorithms must be used. All doses should be reported in terms of dose-to-water and not in terms of dose-to-medium. Successful treatment planning will require accomplishment of all of the following criteria: These criteria will be assessed on dose calculated independently for each lesion (i.e., not from composite dose calculations) if more than 1 lesion is present.

1. **Normalization:** The treatment plan should be initially normalized such that 100% corresponds to the maximum dose within the PTV (MAXPTV). While this point will typically correspond to the PTV center of mass, it can be located elsewhere within the PTV.
2. **Prescription Isodose Surface Coverage:** The prescription isodose surface will be chosen such that 95% of the target volume (PTV) is conformally covered by the prescription isodose surface. Doses less than 95% of the prescription dose are restricted to the outside edges of the PTV. The prescription isodose surface selected MUST be $\geq 60\%$ and $\leq 90\%$ of the dose maximum within the PTV (MAXPTV). The MAXPTV corresponds to the normalization point (100%) of the plan as noted in number 1 above.
3. **Target Dose Heterogeneity:** Rather than prioritizing target dose homogeneity, HIGRT treatment planning prioritizes adequate minimum target coverage and rapid dose fall-off gradients outside of the target. Hot spots within targets are generally accepted without consequence since targets are mostly tumor. The only exception is when the hotspot within the PTV also intersects an OAR.
4. **Critical Organ Doses:** Respect all critical organ dose-volume limits listed below
5. **High-Dose Spillage:**

- a. **Location:** Any dose > 105% of the prescription dose should occur within the PTV and not within the normal tissues outside the PTV.
- b. **Volume:** Acceptable isodose distributions should be as conformal as possible. To this end the ratio of prescription isodose volume to PTV should be as small as possible.
 - i. The ratio of the prescription isodose volume to the PTV volume should ideally be < 1.2.
 - ii. Guidelines for the ratio of the 50% prescription isodose volume to the PTV volume (R50%) and for the maximum dose at 2cm (D2cm) from the PTV. Because it may become more difficult to restrict the 50% isodose volume when dose is summed from treatment of multiple lesions, this ratio should be evaluated for dose calculated for a single lesion (i.e., not for composite dose). Additionally, the 50% isodose volume may be elongated deliberately in order to avoid OAR thereby making it difficult to meet the constraint guidelines. This is acceptable as long as normal tissue constraints are met.

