6.1 Inclusion Criteria

1. Patient has signed informed consent
2. HCC diagnosed either by histology/pathology or Liver Imaging Reporting and Data System (LIRADS 5 per the ACR's LIRADS criteria¹⁰) by CT or MRI
3. Patient is 18 years or older
4. ECOG Performance status of 0-2
5. Child Pugh score A5, A6, B7 or B8 (see Appendix)
6. Lesion \leq 5cm in size
7. \leq 3 lesions in the liver to be treated on protocol
8. Lesion amenable to treatment with both PLA and HIGRT; for PLA treatment this requires the lesion be visible via ultrasound and/or non-contrast CT or feasible per treating physician

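### As worded, section 8.6.2 judges organ-at-risk limits lesion by lesion, so a plan for two or three lesions can pass while the summed organ dose exceeds a recommended limit

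*Combined protocol and SAP*

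**What the plan says.** Section 8.6.2 opens its list of plan criteria with "Successful treatment planning will require accomplishment of all of the following criteria". The next sentence, which applies when a patient has more than one lesion, reads "These criteria will be assessed on dose calculated independently for each lesion (i.e., not from composite dose calculations". Five numbered criteria follow: normalization, prescription coverage, target heterogeneity, organ doses and high-dose spillage. Criterion 4 is "Respect all critical organ dose-volume limits listed below", which points to the tables in section 8.7. It is not exempted from the per-lesion sentence.

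Section 6.1 allows up to "3 lesions in the liver to be treated on protocol", each no larger than 5 cm.

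Composite dose comes up in one other place, under criterion 5. For the 50% isodose ratio (R50%) the protocol says "this ratio should be evaluated for dose calculated for a single lesion (i.e., not for composite dose", and gives a reason specific to that ratio. It then tolerates a deliberately elongated 50% isodose volume: "This is acceptable as long as normal tissue constraints are met". It does not say whether those constraints are judged on single-lesion or summed dose.

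Section 8.7 presents its limits as recommendations that the treating physician may modify. They include a mean liver dose of 13 Gy in the 10-fraction table. Section 8.6 assigns 10 fractions to Child-Pugh B patients, among others, with the final choice left to the physician.

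**The concern.** An organ at risk receives the sum of what every lesion's plan delivers. A rule that judges organ limits on each lesion's dose alone does not measure the quantity that the limits are meant to control.

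The protocol relies on those limits for safety. Section 7.1.4 states: "Prior retrospective studies have been used to define our current dose limitation guidelines to reduce risk of RILD to a negligible level". That reassurance can hold only for the dose the liver actually receives. Section 7.1.3 lists liver damage leading to liver failure among the rare but very serious HIGRT risks, and the 13 Gy figure sits in the table for the schedule assigned to Child-Pugh B patients.

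A site that follows section 8.6.2 to the letter could therefore accept a plan whose total is above the recommended figure, with nothing prompting the physician to look at that total.

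**Working it through.** The plan gives no summed-dose figure to reproduce. The check is a reading of the text, followed by dose addition.

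**1. Scope of the instruction.** The per-lesion sentence refers to the criteria just announced, and criterion 4 is one of the five. No section asks for organ limits to be met on summed dose.

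**2. Break-even for mean liver dose.** The mean over one liver is additive across plans. With *k* equal plans, the total exceeds 13 Gy once each gives more than 13/*k*:
- two lesions: 13/2 = 6.5 Gy each
- three lesions: 13/3 = 4.33 Gy each

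Equal plans therefore pass singly and fail in total from above 6.5 up to 13 Gy each (two) or from above 4.33 up to 13 Gy each (three). For example, an assumed 7 Gy from each of two plans passes twice and totals 14 Gy.

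**3. Can eligible patients reach this?** Inputs from the protocol: 50 Gy prescribed and margins of 5-10 mm radially and 7-10 mm superior/inferior (section 8.6); coverage such that "95% of the target volume (PTV) is conformally covered by the prescription isodose surface" (section 8.6.2); at most three lesions of at most 5 cm (section 6.1).

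Assumptions: spherical lesions, no added motion margin, PTVs wholly inside the liver and not overlapping, the uncovered 5% counted as 0 Gy, no dose outside the PTV, and liver volume *L*, which the documents do not give.

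PTV of a 5 cm lesion:
- smallest margins: 4/3 × π × 3.0 × 3.0 × 3.2 = 120.6 cc
- largest margins: 4/3 × π × 3.5³ = 179.6 cc

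Mean liver dose per lesion = 0.95 × 50 × PTV / *L*. For *L* = 1,500 cc: 47.5 × 120.6/1,500 = 3.82 Gy and 47.5 × 179.6/1,500 = 5.69 Gy.

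The last column takes the mean over liver minus GTV instead. With a GTV of 65.4 cc per lesion, the formula is 3 × 50 × (0.95 × PTV − 65.4)/(*L* − 196.3).

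| Assumed *L* | One 5 cm lesion (Gy) | Two (Gy) | Three (Gy) | Three, liver minus GTV (Gy) |
|---|---|---|---|---|
| 1,200 cc | 4.78-7.11 | 9.55-14.22 | 14.33-21.33 | 7.35-15.72 |
| 1,500 cc | 3.82-5.69 | 7.64-11.37 | 11.46-17.06 | 5.66-12.10 |
| 1,800 cc | 3.18-4.74 | 6.37-9.48 | 9.55-14.22 | 4.60-9.84 |

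A single lesion is well under 13 Gy in every row. Three 5 cm lesions exceed 13 Gy on PTV dose alone when *L* is below 3 × 47.5 × PTV/13, that is 1,322 cc with the smallest margins and 1,969 cc with the largest.

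For 3 cm lesions the PTV is 36.9-65.4 cc. Three of them give 2.92-7.77 Gy over the three liver volumes, which is below 13 Gy throughout.

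**4. Other limits.** Near-maximum limits for serial organs add only where the high-dose regions of the plans overlap, so the mean liver dose is the clearest case.

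**The case against.** Context favours a benign intent. Section 8.7 states its limits for a regimen and uses whole-organ quantities such as mean liver dose and total kidney. The separate single-lesion rule for R50% would be redundant if the opening sentence already covered everything, and the same paragraph treats normal tissue constraints as a backstop. I accept that the sentence was probably aimed at target and conformity measures. But the text does not say so, and under its literal wording the backstop is per lesion as well.

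The limits are also recommendations open to physician discretion. That stands, but it does not remove the gap: discretion works only when the excess is seen, and a total that nobody is asked to compute prompts nothing.

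The breach cases are demanding. Two 5 cm lesions do not reach 13 Gy on PTV dose alone at 1,500 or 1,800 cc, and three 3 cm lesions do not reach it at any of the volumes tried. Averaged over liver minus GTV, three 5 cm lesions exceed 13 Gy only at 1,200 cc, towards the larger margins. Any PTV volume outside the liver or overlapping another PTV lowers the figures. This limits the practical weight of the point, although dose outside the PTV, here counted as zero, works in the other direction.

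A reader might infer that the protocol forbids a composite check, that patients will in fact be overdosed, or that the QOL comparison is compromised. The documents support none of these. They say how the criteria are assessed without barring a further check, they give no organ doses and no number of multi-lesion patients, and nothing links this wording to the primary analysis or its power.

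**Conclusion.** The point holds as a defect of wording that bears on patient safety. Read literally, section 8.6.2 excludes summed dose from the organ-limit check in exactly the patients for whom summation matters, and no other section restores it.

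The break-even values of 6.5 and 4.33 Gy per lesion follow from the protocol's own 13 Gy and need only equal plans. The illustration for a 1,500 cc liver (3.8-5.7 Gy for one lesion, 7.6-11.4 Gy for two, 11.5-17.1 Gy for three) rests on the assumed liver volume and geometry. It shows that a breach is possible within eligibility, mainly with three large lesions, and it does not estimate how often one would occur. I am confident of the literal reading and only moderately confident of the practical effect. The change is worth making because it is cheap and the harm it guards against is serious.

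**What to change.** In section 8.6.2:
- restrict the per-lesion instruction to criteria 1, 2, 3 and 5
- state that criterion 4 and the section 8.7 limits are assessed on the composite dose from all lesions treated on protocol
- state that any modification approved by the physician is judged against that composite dose
- record composite organ doses for patients with more than one treated lesion

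This keeps the physician's discretion and applies it to the dose the organ receives. The cost is a few sentences and some extra data fields for multi-lesion patients. The downside is that some multi-lesion plans may need reworking.
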